12.2.2 Power Calculations for Continuous Variables in the Case Control Study

Formulas for the calculation of study size and power for continuous variables have been developed by Walter (Walter, 1980) and by Lubin, Gail and Ershow (Lubin et al, 1988). Here, the derivations of Lubin et al. will be used to evaluate the operating characteristics of this study. The general sample size formula used in this evaluation is:

$$N \stackrel{!}{=} \frac{(\hat{e}\%1)}{\hat{e}} \frac{[Z_{a} \acute{o}_{x} \% Z_{a} \{(\hat{e}\acute{o}_{1}^{2}\%\acute{o}_{o}^{2})/(\hat{e}\%1)\}^{1/2}]^{2}}{(\mu_{1}\&\mu_{o})^{2}}$$

where

$$\acute{o}_{\div}^2 \ ' \ (\acute{o}_1^2 \, \% \, \acute{e} \acute{o}_0^2) / (\acute{e} \% 1) \, \% (\mu_1 \, \& \mu_0)^2 \acute{e} / (\acute{e} \% 1)^2$$

and

$$\mu_{i}' \left\{ mxf(x)P(D' i^{*}x)dx \right\} \left\{ mf(x)P(D' i^{*}x)dx \right\}^{\&1}$$
$$\delta_{i}^{2'} \left\{ mx^{2}f(x)P(D' i^{*}x)dx \right\} \left\{ mf(x)P(D' i^{*}x)dx \right\}^{\&1} \&\mu_{i}^{2}$$

In the above formula, μ_1 and \dot{o}_1^2 are the mean variance of the case exposure variable and μ_0 and \dot{o}_0^2 are the mean and variance of the control exposure variable. The proposed number of cases and controls is large enough to detect small effects (either in terms of linear risk or in terms of exponential risk). As such, the above formula can be simplified to:

N'
$$\frac{(\hat{e}\%1)(Z_{\dot{a}}\%Z_{\hat{a}})^2 \acute{o}^2}{\hat{e}(\mu_1 \& \mu_0)^2}$$

This simplification occurs because as the effect size gets small, $\dot{o}_{\pm}^2 \cdot \dot{o}_{1}^2 \cdot \dot{o}_{0}^2 \cdot \dot{o}^2$. This formula can be rearranged to determine the effect size $(\mu_1 \& \mu_0)/\dot{o}$ that can be detected with specified alpha level, power, and number of case control pairs. With the proposed of 720 cases and 720 controls, there will be better than 90% power to detect effect sizes of at least 0.16 standard deviations, a small effect size.

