6.3.1 Random Digit Dialing Controls

Cases are matched in a one to one ratio to controls selected through random digit dialing. Random digit dialing facilitates the selection of a control group that approximates a probability sample in the population. Random digit dialing (RDD) is used to identify potential controls through an unbiased clustered random sample of households with telephones (Waksberg, 1978). Cluster sampling of telephone households and a stratified sample of age-, gender-, and self-identified racematched individuals are used (Hartge et al, 1984).

The groups selected to generate telephone numbers, Survey Sampling Inc. (SSI), and to perform the telephone recruitment of potential controls, Telesurveys Research Associates (Random Digit Dialing (RDD) Interview Group), work under the direction of the Clinical Coordinating Center. The RDD callers are responsible for making initial telephone contact with potential controls in the geographic areas of the Clinical Centers.

Once the RDD Interview Group recruiter has established the eligibility, availability and willingness of the potential control to participate, the potential control is informed that an interviewer from the Clinical Center will be in touch soon to set up an appointment to meet for questionnaire

administration and phlebotomy. Potential controls are informed that a payment will be given to them after they complete the study interview to reimburse them for parking costs, meals and other expenses (including lost time from work) at the medical center, and transportation costs.

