Tables 1 and 2 show the power of the proposed design to detect specified odds ratios as a function of the correlation (0.5 and 0.0) between case and control exposure rates, and the expected value of the control exposure rate with the alpha level for the test set at 0.05 (two sided test) and with 720 cases. With the proposed number of cases and controls there will be 98.6% power to detect odds ratios of 0.7 or less and 98.8% power to detect odds ratios of 1.4 or greater when the correlation between case and control exposures is 0.5 (Table 1) and the proportion of controls exposed is 0.3. If the correlation between cases and control exposures is 0.0 (a conservative estimate), the power is reduced to 84.3% and 85.1%, respectively. If the proportion of controls exposed is reduced to 0.05 there is at least 90% power to detect an odds ratio of 2.0.

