factor also present and at the same level of magnitude in males or is it different. For binary exposure variables a matched case control regression model will be used with terms for the subgroup, the exposure, and the exposure-subgroup interaction in the model. For a case control design with one case and one control, the Cox Proportional Hazards model can be used by creating a dummy variable that always lists the case and "failing" first with control "censored" after the case "failure time". Power calculations for the factorial term in the Cox Model have been published (Peterson and George, 1993). In general the statistical efficiency of the interaction test is lower than the main effects test. For instance, with 50% of the population in one subgroup and 50% in the complimentary subgroup, the efficiency of the interaction test is one half that of the main effects test.

As an example, the current study design has at least 80% percent power to detect an odds ratio of 1.25 when the exposure variable of interest has a 30% prevalence and the test is being performed at the 5% alpha level. Now let us consider a statistical interaction test of an exposure between two groups. The test would be designed to determine if the ratio of the two odds ratios in the two groups were different or the same. Specifically, the interaction test is a test of whether the ratio of these two odds ratios is one. To be able to detect a ratio of the two odds ratios that is 1.25 or larger with 80% power with an exposure variable with a 30% prevalence and testing at the 5% alpha level would require twice the number of case control pairs or 1,440 cases. With 720 cases, there is at least 80% power to detect a ratio of two odds ratios on the order of magnitude of 1.38. This is not substantially different from the operating characteristics of the main effect comparisons. Thus there will be adequate power to detect small interactions with the proposed sample size.

For continuous variables, there is little impact on the power of proposed analyses to detect meaningful differences between case and control means in each of the above subgroup sizes. With 180 cases in a subgroup, it will be possible to detect differences of 0.34 standard deviations with 90% power when testing at alpha 0.05 (two sided test).

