12.4 CONCLUSIONS

The methods for the major analyses for the case control study and the clinical course are presented in this chapter. For the case control study of cases with sarcoidosis and age-gender-race matched controls, a matched case control design has been proposed. Key issues in this design are control of bias and confounding. Control of confounding primarily depends upon the selection of adequate adjustment techniques. The proposed approach is to use non-parametric techniques such as the Mantel-Haenzel test for matched pairs, and conditional logistic regression for more complex analyses. For measurements that will be collected serially over time, longitudinal data analysis methods have been proposed. These methods are robust in that they will allow for differential numbers of observations for each case, correct for missing data, and unanticipated variance-covariance structures for the repeated measurements without loss of statistical validity in testing.

A preliminary power analysis has been performed for the proposed study. It has been found that the proposed number of cases and controls (at least 720 and 720) is sufficient to allow for small effects to be detected with adequate power (90%) when testing at the alpha level of 0.05 (two-sided tests). The proposed number of cases and controls is large enough to allow for subgroup analyses. The proposed number of cases is also sufficient to allow for the detection of moderate differences in means in the longitudinal follow-up study. There will be adequate power to detect small effect sizes (0.70 ó) when testing at the 0.05 level and when making comparison of the five sarcoidosis groups.

		Table 1 Power of Case - Control Comparisons alpha=0.05 and N=720 Correlation (p1,p0)=0.5									
Odds	Ratio	0.01	0.025	Proj 0.05	portion 0.1	of Con 0.3	trols E 0.5	xposed 0.7	0.9		
	0.3	0.580	0.927	0.998	1.000	1.000	1.000	1.000	1.000		
	0.5	0.324	0.658	0.914	0.996	1.000	1.000	1.000	1.000		
	0.6	0.217	0.458	0.739	0.951	1.000	1.000	1.000	0.993		
	0.7	0.136	0.273	0.477	0.751	0.986	0.997	0.994	0.860		
	0.8	0.081	0.141	0.234	0.401	0.760	0.844	0.796	0.463		
	0.9	0.046	0.063	0.087	0.129	0.248	0.292	0.257	0.137		
	1.0	0.025	0.025	0.025	0.025	0.025	0.025	0.025	0.025		
	1.1	0.045	0.060	0.082	0.119	0.218	0.247	0.212	0.114		
	1.2	0.073	0.122	0.197	0.329	0.623	0.682	0.592	0.291		
	1.3	0.112	0.213	0.366	0.599	0.907	0.936	0.876	0.512		
	1.4	0.160	0.327	0.556	0.817	0.988	0.993	0.976	0.706		

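### Section 12.2.2: with 720 pairs, the printed formula gives about 86% power at 0.16 SD, not better than 90%; its 90% point is 0.171 SD

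*Protocol*

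**What the plan says.** Section 12.2.2 gives a general sample size formula for a continuous exposure and reduces it, for small effects, to a simple expression in the number of controls per case, the two normal deviates, a common variance and the difference in means. It says the expression can be solved for the detectable effect size and then states the result. "With the proposed of 720 cases and 720 controls", the text continues, "there will be better than 90% power to detect effect sizes of at least 0.16 standard deviations, a small effect size".

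Section 12.2.3 gives the companion figure for a subgroup: "With 180 cases in a subgroup, it will be possible to detect differences of 0.34 standard deviations with 90% power". The same sentence fixes alpha at 0.05, two-sided.

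Section 12.2.2 does not name its own alpha, but the neighbouring sections do. Section 12.2.1 has the "alpha level for the test set at 0.05 (two sided test) and with 720 cases", and section 12.4 sums up the power analysis at 90% power and two-sided 0.05. On allocation, section 6.3.1 says "Cases are matched in a one to one ratio to controls selected through random digit dialing".

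**The concern.** Under the simplified formula the detectable effect is proportional to one over the square root of the number of pairs. Going from 180 to 720 pairs should therefore exactly halve it. Half of 0.34 is 0.17, yet section 12.2.2 states 0.16 and adds that power is better than 90% there. Both figures cannot be right on the same basis.

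The sentence in section 12.2.2 is the only full-sample power figure the protocol gives for a difference in continuous means between cases and controls. Anyone judging what the etiology study can detect on a continuous exposure or scale score will take it from there.

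**Working it through.** **Inputs**
- Pairs: 720 (section 12.2.2) and 180 (section 12.2.3).
- Controls per case: κ = 1 (sections 6.3.1 and 12.2.1).
- Alpha: 0.05 two-sided, so Zα = 1.960 (sections 12.2.1, 12.2.3 and 12.4).
- Power: 90%, so Zβ = 1.2816.
- d = difference in means divided by the SD.

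**Formula (section 12.2.2, simplified form)**

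N = (κ+1)(Zα+Zβ)²σ² / [κ(μ1−μ0)²]. With κ = 1 this is N = 2(Zα+Zβ)²/d², so d = √[2(Zα+Zβ)²/N]. Here (1.960+1.2816)² = 10.507.

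**Step 1: the 180-pair figure**

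d = √(2 × 10.507/180) = 0.342. Power at 0.34 SD is 89.7%. The figure in section 12.2.3 reproduces.

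**Step 2: the 720-pair figure**
- Detectable effect at 90%: d = √(2 × 10.507/720) = 0.171.
- Power at 0.16 SD: Φ(0.16 × √360 − 1.960) = Φ(1.076) = 85.9%.
- Pairs needed for 90% at 0.16 SD: 2 × 10.507/0.0256 = 821, which is 14% more than 720.
- Power at 0.17 SD: 89.7%, as for 0.34 SD with 180 pairs.

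**Step 3: could another reading give the stated figure?**

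| Reading, 720 pairs, 0.16 SD | Power |
|---|---|
| Simplified formula, two-sided 0.05 | 85.9% |
| General formula of section 12.2.2 | 85.8% |
| Two-sample t-test | 85.9% |
| Paired t-test, zero correlation | 85.8% |
| One-sided 0.05 | 91.8% |
| SD taken as that of the paired difference | 99.0% |

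- *Rounding.* Values that round to 0.16 stop at 0.165, where power is Φ(0.165 × √360 − 1.960) = Φ(1.171), about 88%. Values that round to 0.34 (0.335 to 0.345) halve to 0.1675 to 0.1725.
- *One-sided test.* The protocol specifies two-sided tests, and a one-sided calculation would make the 180-pair figure 0.308 SD instead of 0.34.
- *SD of the paired difference.* The formula carries the factor (κ+1)/κ = 2 on a common variance, so its SD is that of the exposure, not of the difference. On the other reading, power at 0.34 SD with 180 pairs would be 99.5%, which does not match section 12.2.3 either.

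**Step 4: within-pair correlation ρ**

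For a paired test the variance of the difference is 2σ²(1−ρ), so 90% power at 0.16 SD needs ρ = 1 − 0.0256 × 720/(2 × 10.507) = 1 − 18.432/21.015 = 0.123. At ρ = 0.5, power at 0.16 SD is about 99%. But ρ = 0.123 would also move the 180-pair figure to √(2 × 0.877 × 10.507/180) = 0.32 SD. None of the bases tried gives both 0.16 and 0.34 as 90%-power effect sizes.

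**The case against.** The strongest reply is that the planned analysis is a paired t-test (section 12.3.2.2). Section 12.2.1 expects matching to induce positive correlation and treats zero as the conservative value. With a correlation of about 0.12 the stated figure would be met, and at 0.5, the value used for binary exposures in Table 1, it would be exceeded comfortably. This stands as a limit on the consequence. It does not rescue the sentence, because section 12.2.2 derives its figure from a formula without a correlation term and names no correlation for continuous variables.

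A reader might infer that the study's real type II error at 0.16 SD is about 14% where under 10% was promised. The documents do not support that as a property of the study. The 14% (100 − 85.9) belongs to the printed formula at exactly 0.16 SD with zero correlation; the true correlation is not given.

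A reader might also take this as the only power stated for every continuous or psychosocial comparison. It is not. Section 12.2.3 states another for 180 pairs. In section 3.5, the first hypothesis concerns only cases with symptomatic disease, who may number fewer than 720, and the other two concern associations and prediction, not case-control mean differences.

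Finally, the gap is 0.011 SD, both values are small effects, and section 1.5.1 justifies 720 pairs by binary exposures. All of this is correct and bears on weight, not on whether the sentence is wrong.

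**Conclusion.** The statement in section 12.2.2 is wrong as written. Under its own simplified formula, with 720 pairs, 1:1 matching and two-sided alpha 0.05, power at 0.16 SD is 85.9%, about 4 percentage points short of the claim. The effect detectable with 90% power is 0.171 SD, so the stated effect is about 6% too small (0.160/0.171 = 0.94). The figure also conflicts with the correct 180-pair figure in section 12.2.3.

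The result rests on two things: two-sided 0.05, which section 12.2.2 does not repeat but sections 12.2.1, 12.2.3 and 12.4 all use; and zero within-pair correlation, which is what the formula implies. It would be too much to conclude that the study is underpowered for continuous variables or that 720 pairs is too few. The paired analysis may well do better than the formula, and no design choice, test or planned conclusion depends on 0.16 as against 0.17 SD.

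**What to change.** In section 12.2.2, replace the sentence with wording to this effect:

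> With 720 pairs there is about 90% power to detect 0.17 standard deviations (about 86% for 0.16) at two-sided alpha 0.05, assuming no within-pair correlation. Power of the paired t-test is higher if the correlation is positive; 90% at 0.16 standard deviations needs a correlation of about 0.12.

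If the investigators prefer to keep 0.16 SD, they should state and justify the correlation behind it and restate the 180-pair figure in section 12.2.3 on the same basis. Otherwise section 12.2.3 needs no change.

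The cost is one sentence and a slightly less favourable headline figure. Sample size and analysis are unaffected.

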12.2.3 Subgroup Analyses

As part of ACCESS, Clinical Center investigators may want to make comparisons of cases and controls within certain strata. For instance, there could be comparisons of female cases and controls, comparisons of black cases and controls, and comparisons of erythema nodosum cases with their matched controls. Each of these subgroup comparisons will bring with it a different number of cases and controls and power for making comparisons. Effect sizes that could be detected in one subgroup analysis, might not be detected in another analysis. Power analyses have been performed for statistical comparisons that will be performed in subgroups representing 7%, 14%, 25%, 50% and 75% of the entire case control study population. These percentages may be representative of comparisons for a small substudy (7% and 14%), within a sarcoidosis category (20%), within a gender comparison (50%), and within the black population (75%, published reports put the percentage of sarcoidosis cases who are black between 60% and 80% in some cities). Power calculations for binary exposure variables when performing analyses in subgroups are presented in Tables 3 through 12. There is a substantial change in the odds ratios that can be detected with adequate power depending upon the number of cases in the subgroup. For instance, fixing the odds ratio at 0.7, the correlation between case-control response at 0.5, and the proportion of controls exposed at 0.3, there is 54.8%, 83.7% and 95.0% power to detect this odds ratio for 180, 360 and 540 case control pairs, respectively.

As part of each subgroup analysis, a statistical test will be performed to determine if the findings relating to exposures in one subgroup correspond to the findings in the complimentary subgroup (an interaction test). For instance if a risk factor is discovered for females, is that risk

factor also present and at the same level of magnitude in males or is it different. For binary exposure variables a matched case control regression model will be used with terms for the subgroup, the exposure, and the exposure-subgroup interaction in the model. For a case control design with one case and one control, the Cox Proportional Hazards model can be used by creating a dummy variable that always lists the case and "failing" first with control "censored" after the case "failure time". Power calculations for the factorial term in the Cox Model have been published (Peterson and George, 1993). In general the statistical efficiency of the interaction test is lower than the main effects test. For instance, with 50% of the population in one subgroup and 50% in the complimentary subgroup, the efficiency of the interaction test is one half that of the main effects test.

As an example, the current study design has at least 80% percent power to detect an odds ratio of 1.25 when the exposure variable of interest has a 30% prevalence and the test is being performed at the 5% alpha level. Now let us consider a statistical interaction test of an exposure between two groups. The test would be designed to determine if the ratio of the two odds ratios in the two groups were different or the same. Specifically, the interaction test is a test of whether the ratio of these two odds ratios is one. To be able to detect a ratio of the two odds ratios that is 1.25 or larger with 80% power with an exposure variable with a 30% prevalence and testing at the 5% alpha level would require twice the number of case control pairs or 1,440 cases. With 720 cases, there is at least 80% power to detect a ratio of two odds ratios on the order of magnitude of 1.38. This is not substantially different from the operating characteristics of the main effect comparisons. Thus there will be adequate power to detect small interactions with the proposed sample size.

For continuous variables, there is little impact on the power of proposed analyses to detect meaningful differences between case and control means in each of the above subgroup sizes. With 180 cases in a subgroup, it will be possible to detect differences of 0.34 standard deviations with 90% power when testing at alpha 0.05 (two sided test).

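### For a 50/50 subgroup split the interaction test has one quarter, not one half, of the main-effect efficiency, so on the protocol's own base the power for a ratio of odds ratios of 1.38 is about 52%, not at least 80%

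*Protocol*

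**What the plan says.** Protocol section 12.2.3 defines the interaction test as a test that the ratio of two subgroup odds ratios equals one. Its worked example runs as follows.

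- Main effect: "the current study design has at least 80% percent power to detect an odds ratio of 1.25". This is for 30% exposure and a 5% alpha.
- Efficiency: for a split into two equal halves, it states that "the efficiency of the interaction test is one half that of the main effects test".
- Sample size: it follows that a study aiming at 80% power for a ratio of odds ratios of 1.25 "would require twice the number of case control pairs or 1,440 cases".
- Power at the planned 720 pairs: "there is at least 80% power to detect a ratio of two odds ratios on the order of magnitude of 1.38".

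The section then concludes that interaction tests perform much like main-effect tests and that the study is adequately powered for small interactions. The example does not state the case-control exposure correlation it assumes. Section 12.2.1 tabulates two values, 0.5 and 0.0, "with the alpha level for the test set at 0.05 (two sided test) and with 720 cases".

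**The concern.** The interaction test compares two estimates, each from half the pairs. Halving the pairs doubles the variance of each estimate, and taking the difference of two independent estimates doubles it again. The example counts only one of these two doublings.

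The interaction test has a working role in this protocol. Section 12.2.3 attaches one to every subgroup analysis. Section 12.3.2.2 uses interaction terms to judge whether odds ratios are alike in males and females or in blacks and whites. Section 1.5.1 lists tests for interaction among the benefits of the sample size. Anyone who relies on the stated 80% would give a non-significant interaction more weight than it deserves.

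**Working it through.** **Inputs.** Pairs N = 720, two-sided alpha 0.05 (z = 1.96), one control per case, control exposure p0 = 0.30, correlation r = 0.5 or 0 (section 12.2.1); odds ratio 1.25, ratio of odds ratios 1.38, 50/50 split (section 12.2.3).

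**Formula (section 12.2.1, one control per case).** Power = Φ(|p1 − p0|·√N / √ψ − 1.96), with p1 = OR·p0 / (1 + (OR − 1)·p0) and ψ = p1 + p0 − 2·p1·p0 − 2·r·√(p1·q1·p0·q0), where q = 1 − p.

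**1. The formula reproduces the protocol.** At N = 720 and p0 = 0.3 it gives 98.6% and 98.8% for odds ratios 0.7 and 1.4 at r = 0.5, and 84.3% and 85.1% at r = 0. For odds ratio 0.7 at r = 0.5 with 180, 360 and 540 pairs it gives 54.8%, 83.7% and 95.0%. All match the text.

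**2. The example's base is r = 0.5.** For odds ratio 1.25, p1 = 0.375/1.075 = 0.3488 and the difference is 0.0488.
- r = 0.5: ψ = 0.2211; Φ(0.0488·26.83/0.4702 − 1.96) = Φ(0.83) = 79.6%, the stated 80% after rounding.
- r = 0: ψ = 0.4395; power 50.7%.

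**3. Where 1.38 comes from.** Half efficiency means an effective N of 360. At r = 0.5 a ratio of 1.38 then has 81.4% power. Equivalently, 1.25^√2 = 1.37. The protocol's figure is therefore the product of the one-half factor.

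**4. The correct factor.** Let V be the variance of the 720-pair log odds ratio.
- Each 360-pair estimate: 2V.
- Difference of the two: 2V + 2V = 4V.
- Efficiency relative to the 720-pair main effect: V/4V = 1/4, an effective N of 180.

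**5. Corrected figures.** For a ratio of 1.38, p1 = 0.414/1.114 = 0.3716 and the difference is 0.0716. At r = 0.5, ψ = 0.2272, and Φ(0.0716·13.42/0.4767 − 1.96) = Φ(0.06) = 52.2%.

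| Quantity (50/50 split) | Protocol | r = 0.5 | r = 0 (sensitivity) |
|---|---|---|---|
| Power at ratio 1.38, 720 pairs | at least 80% | 52% | 30% |
| Ratio detectable at 80%, 720 pairs | 1.38 | about 1.56 | about 1.87 |
| Pairs for ratio 1.25 at 80% | 1,440 | about 2,900 | about 5,790 |
| Power at ratio 1.25, 1,440 pairs | 80% | 50% | 29% |

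For the third row, a main effect of 1.25 needs (1.96 + 0.8416)²·ψ/(p1 − p0)² pairs. That is about 728 at r = 0.5 and 1,447 at r = 0, each multiplied by 4.

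**6. Cross-checks.** Taking the protocol's 80% at face value, SE(main) = ln 1.25/2.8016 = 0.0797 and SE(interaction) = 2 × 0.0797 = 0.159. Power at 1.38 is then Φ(0.322/0.159 − 1.96) = 52%, and the detectable ratio is 1.25² = 1.56. A direct comparison of two log odds ratios with 360 pairs each gives 50.6% to 53.0% at r = 0.5 and 28.7% to 30.1% at r = 0, depending on where the two odds ratios lie. On the difference-in-proportions scale the r = 0.5 range is 51% to 58%.

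**The case against.** **Could the stated factor be right on another reading?** One half is correct if the interaction is compared with the effect in a single 360-pair subgroup, but the example compares it with the 720-pair main effect. If efficiency meant a ratio of standard errors, one half would be correct, but that implies four times the pairs and the text says twice. The source cited for the factorial term cannot be consulted here. It would not rescue the conversion to 1,440, which is the protocol's own step.

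**Does it matter?** The paragraph is illustrative. The 720 pairs rest on main effects (sections 1.5.1 and 12.2.1), the section already concedes that interaction tests are less efficient, confidence intervals and interaction terms are planned (section 12.3.2.2), and section 3.7 describes the study as generating hypotheses. All of this stands. It means that the design and analysis need not change, but it does not make the figures correct. Nor does any section say that a null interaction will be reported as proof of a common effect; that is a risk, not a stated plan.

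**Stronger readings that a reader might infer, and that the documents do not support:**
- *That 52% is a ceiling.* It is the value at r = 0.5, the higher of two tabulated correlations. The same formula gives about 61% at 0.6, 73% at 0.7 and 80% at 0.75.
- *That the efficiency error alone takes power to about 30%.* The error takes it from about 81% to 52%. The rest comes from assuming r = 0, and section 12.2.1 expects matching to produce positive correlation.
- *That the same factor governs gene-by-exposure interactions.* The derivation needs strata shared by both members of a pair, such as sex or race. Genotype is not a matching variable and can differ within a pair.
- *That only large interactions are detectable.* Sections 1.5.1 and 1.5.2 call odds ratios of about 3 moderate, so a ratio of 1.56 to 1.87 is not large in the protocol's own terms.

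**Conclusion.** Section 12.2.3 is wrong as written. With two equal subgroups the efficiency is one quarter, and every figure that depends on one half is too favourable. On the protocol's own base, power at a ratio of 1.38 is overstated by nearly 30 percentage points and the pairs needed for a ratio of 1.25 are understated by a factor of two. The conclusions that interaction and main-effect power are much alike, and that small interactions are covered, do not follow.

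The result assumes strata shared within pairs, an equal split, similar information per pair in the two strata (similar exposure prevalence and discordance), 30% exposure and correlation 0.5. Correlation 0 is a separate sensitivity, under which the base claim for an odds ratio of 1.25 also falls to about 51%. The finding concerns stated power. It does not show that 720 pairs are too few for the main effects or that the planned interaction test is invalid.

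**What to change.** In section 12.2.3:

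1. Replace one half with one quarter, for matched-variable subgroups such as sex or race with a 50/50 split and similar information per pair.
2. Replace 1,440 with about 2,900, and 1.38 with about 1.56.
3. State that these figures, and the base odds ratio of 1.25, assume correlation 0.5. Give the correlation-0 values beside them: about 51% power for odds ratio 1.25, about 30% for a ratio of 1.38, a detectable ratio of about 1.87, and about 5,790 pairs for a ratio of 1.25.
4. Delete the statements that interaction power is close to main-effect power and adequate for small interactions. State the detectable ratio instead, without a new adjective.

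The cost is a text correction and a less favourable stated figure. Sample size, test and analysis method are unchanged.

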12.2 POWER CALCULATIONS

12.2.1 Power Calculations for the Case Control Study

Determination of power for matched pair designs have been developed by Miettinen (Miettinen, 1969) and Walter (Walter, 1980) and more recently by Lubin, Gail, and Ershow (Lubin et al, 1988). These formulas can be used to evaluate the adequacy of the number of cases and controls in the case control design.

For binary exposure variables analyzed as part of the case control study the formula for power is the following:

power '
$$\ddot{O}\left(\frac{\ddot{a}@\hat{e}@N}{\sqrt{g @\hat{e}@(\hat{e}\%1) N/2}} \& Z_{\dot{a}}\right),$$

where $A_{\overline{k}}$ would be 1.96 ($\dot{a} = 0.05$ two sided test), N is the number of cases, \hat{e} is the number of controls matched to each case ($\hat{e} = 1$ in ACCESS), \ddot{a} is the difference between the expected percentages of cases and controls exposed to the risk factor of interest ($p_1 - p_0$) and \emptyset is the

proportion of case control pairs in which one person's exposure history differs from the other (discordance). Breslow and Day (Breslow and Day, 1980) have shown that only the discordant pairs in a case control study contribute information to the estimation of the odds ratio. Thus, discordant pairs are "informative".

Matched case control study analysis differs from prospective study or clinical trials data analysis. Psi (\emptyset) is dependent upon the degree of correlation between the probability that a case is exposed (has an attribute) and the probability that the control for this case is exposed. This correlation will be a function of the values of the matching covariates and thus the probabilities of exposure will vary from pair to pair and a correlation between these probabilities will be present.

Let p_1 be the expected percentage of exposure in the cases,

p₀ be the expected percentage of exposure in the control,

- and $Cov(p_1,p_0)$ be the expected covariance of the matched case and control exposure probabilities.
- then $\phi = p_1 + p_0 2 p_1 p_0 2 cov (p_1, p_0)$.

This can be rewritten to:

$$a' \frac{1\%\ddot{a}^2}{2} \& 2(p\&0.5)^2 \& 2cov (p_1, p_0)$$

with
$$\overline{p}' = \frac{p_1 \% p_0}{2}$$

Examination of this equation shows that \emptyset will generally be less than 0.55 except when \ddot{a} is very large, and/or the cov (p_1 , p_0) < 0. In general, matching produces positive correlations and it can be expected that there will be less than 55% of case control pairs that are informative.

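### Section 12.2.3 gives 80% as the minimum power for an odds ratio of 1.25 without naming the case-control correlation; it is about 80% at correlation 0.5 and about 51% at correlation 0

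*Protocol*

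**What the plan says.** Section 12.2.3 uses a worked example to introduce the power of interaction tests. It starts from the main effect: "the current study design has at least 80% percent power to detect an odds ratio of 1.25". The conditions attached are an exposure prevalence of 30% and a 5% significance level; no correlation is given. From this start the paragraph derives that detecting a ratio of two odds ratios of 1.25 would take 1,440 pairs, that 720 pairs can detect a ratio of about 1.38, and that power for small interactions is therefore adequate.

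Section 12.2.1 sets the conditions for the main tables: "the alpha level for the test set at 0.05 (two sided test) and with 720 cases". It says that the proportion of discordant pairs "is dependent upon the degree of correlation between the probability that a case is exposed" and the matched control's probability of exposure. It then quotes power under two settings. One applies "when the correlation between case and control exposures is 0.5 (Table 1"; the other, shown in Table 2, is introduced by "If the correlation between cases and control exposures is 0.0 (a conservative estimate". Matching is one to one (Section 6.3.1).

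**The concern.** A statement of minimum power should hold across the assumptions that the protocol itself entertains. This one holds, after rounding, at one of the two tabulated correlations and fails by a wide margin at the one labelled conservative. Section 12.2.1 also has a minimum-power statement, 90% for an odds ratio of 2.0 at 5% exposure. That one is true at correlation 0 (Table 2: 0.909; Table 1: 0.995), so a reader coming from there may take the figure in 12.2.3 as the conservative one.

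An odds ratio of 1.25 is the smallest main effect for which the text claims adequate power, and neither Table 1 nor Table 2 has a row for it, so a reader will rely on the sentence. The paragraph's reassurance about interactions is built on the same figure.

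**Working it through.** **Inputs.** N = 720 pairs, one control per case, two-sided 0.05 (Z = 1.96), control exposure p0 = 0.30, odds ratio 1.25, correlation r = 0.5 or 0 (Sections 12.2.1, 12.2.3 and 6.3.1).

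**Formulae.** With one control per case the expression in Section 12.2.1 reduces to

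power = Φ(δ·√(N/ψ) − 1.96), with δ = p1 − p0 and ψ = p1 + p0 − 2·p1·p0 − 2·cov.

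The protocol does not print how it turns a correlation into a covariance. I took cov = r·√(p1(1−p1)p0(1−p0)). With that choice the formula matches 16 of 16 cells checked in Tables 1, 2, 5 and 7 to three decimals, including 0.986, 0.988, 0.843, 0.851, 0.909 and 0.548.

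**Exposure in cases.** p1 = 1.25 × 0.30 / (1 + 0.30 × 0.25) = 0.375/1.075 = 0.3488, so δ = 0.0488.

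**The protocol's figure (r = 0.5).**
- cov = 0.5 × √(0.3488 × 0.6512 × 0.21) = 0.1092
- ψ = 0.4395 − 0.2184 = 0.2211
- δ√(N/ψ) = 2.787; power = Φ(0.827) = 79.6%
- Table 1 agrees: at 30% exposure it has 0.623 at odds ratio 1.2 (fifth entry of "0.073 0.122 0.197 0.329 0.623 0.682 0.592 0.291") and 0.907 at 1.3.

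**The conservative setting (r = 0).**
- ψ = 0.3488 + 0.30 − 2 × 0.3488 × 0.30 = 0.4395
- δ√(N/ψ) = 1.977; power = Φ(0.017) = 50.7%
- Table 2 agrees: 0.363 at 1.2 and 0.644 at 1.3, so 80% at 1.25 is not possible.

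| | r = 0 | r = 0.3 | r = 0.5 |
|---|---|---|---|
| Power at odds ratio 1.25 | 50.7% | 65.5% | 79.6% |
| Odds ratio with 80% power | 1.37 | – | 1.25 |
| Pairs for 80% power at 1.25 | 1,447 | – | 728 |

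**Other readings of the sentence.** Taking 30% as the mean of case and control exposure gives 49.0% and 77.9% (r = 0 and 0.5). Taking it as the case exposure gives 47.2% and 76.0%. An unmatched two-proportion test gives 50.8%. A Cox-type approximation with 720 events and a 30% split gives 78.3%. A one-sided test gives 63.0% and 87.3%, but Section 12.2.1 specifies two-sided testing.

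**Interaction figures.** I take the protocol's one-half efficiency as given; it is not tested here. The detectable log ratio is then ln(1.25) × √2 × 2.8016 / [δ√(N/ψ)], where 2.8016 = 1.96 + 0.8416.
- r = 0.5: 0.2231 × 1.4142 × 2.8016/2.787 = 0.317, ratio 1.37 (protocol: about 1.38)
- r = 0: 0.2231 × 1.4142 × 2.8016/1.977 = 0.447, ratio 1.56

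The 1,440 pairs are 2 × 720, which fits r = 0.5 (2 × 728 = 1,456). At r = 0 the count would be 2 × 1,447 = 2,894.

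**The case against.** The best defence is that correlation 0.5 was intended. The preceding worked example in the same section fixes the correlation at 0.5 and exposure at 0.3, Section 12.2.1 expects matching to produce positive correlation, and both interaction figures are coherent at 0.5. The dependence on correlation is also disclosed: Section 12.2.1 quotes power under both values and Tables 1 and 2 print them in full. I accept all of this. It shows how the figure arose, but the earlier example concerns a different odds ratio and subgroup sizes, the condition is not carried over, and nothing in the protocol says that the correlation will reach 0.5.

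The protocol's minimum-power wording is also not uniform. Section 1.5.1 claims at least 86% for 180 pairs, which matches Table 7 (correlation 0.5, 0.862) and not Table 8 (0.601). The comparison with the 90% statement therefore shows that a reader could be misled, not that a fixed convention was broken.

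A reader might infer more than the documents support:
- *That the claim fails even at correlation 0.5.* The shortfall is 0.4 points, which is rounding, and Table 1 brackets about 80%. Only Table 2 contradicts the sentence.
- *That the study would miss an odds ratio of 1.25 half the time.* That holds only at correlation 0; at 0.3, power is 65.5%.
- *That the sample size is unjustified.* Section 1.5.1 rests it on odds ratios of two or more at 5% exposure, and Table 2 gives 0.909 for that even at correlation 0. The 1.25 sentence is an example.
- *That null results will be taken to exclude 1.25.* Section 12.3.2.2 plans 95% confidence intervals, which will show what the data exclude.

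**Conclusion.** The sentence is wrong as a statement of minimum power. For 720 pairs, 30% control exposure and two-sided 0.05, power at an odds ratio of 1.25 is about 80% if the case-control correlation is 0.5 and about 51% if it is 0. The second figure rests on the assumption that the protocol itself labels conservative. The interaction claims in the same paragraph inherit the condition: at correlation 0, and with the stated one-half efficiency, the detectable ratio is about 1.56 rather than 1.38. Severity is moderate: a stated power figure needs correcting, but no sample size, analysis or decision rule depends on it. The result assumes that the 30% refers to controls and that correlation enters as in the published tables; the other readings tried under two-sided testing at 30% do not restore 80% as a minimum.

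**What to change.** In Section 12.2.3, replace the sentence with text to this effect: with 720 pairs and 30% exposure, power at an odds ratio of 1.25 is about 80% if the case-control correlation is 0.5 and 51% if it is 0; the smallest odds ratio detectable with 80% power at correlation 0 is about 1.37.

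Changing that sentence alone would leave the rest of the paragraph inconsistent. State there that the 1,440-pair and 1.38 figures also assume correlation 0.5, give about 1.56 as the detectable ratio at correlation 0 under the stated efficiency, and qualify the conclusion on small interactions to match.

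The cost is a few reworded sentences and a less favourable stated figure. Design, data collection and analysis are unchanged.
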